5.0 Study Procedures

5.1 Study Design

RESEARCH DESIGN AND METHODS

The proposed clinical trial is designed to evaluate the efficacy of Aging Back Clinics (ABCs) that approach CLBP in older Veterans as a geriatric syndrome, that is, a final common pathway for the expression of multiple contributors, as compared with Usual Care (UC). In the context of the research proposed, **ABCs are virtual interdisciplinary clinics** that are inserted within the stepped care model shown in Figure 4. Veterans without red flags requiring urgent attention are referred for ABC care that will be **delivered by a specialist provider** that has been trained in use of the algorithms. Both ABC care and UC will be provided for up to 12 months. Those with refractory symptoms may be referred for intensive interdisciplinary pain rehabilitation,

depending on their availability and the Veteran's capacity to participate.

Interventions for ABC care participants are numerous and vary depending on participants' needs. These interventions include but are not limited to CBT, pharmacotherapy, physical therapy (PT), exercise therapy, analgesia, orthotics, injections, and acupuncture. One of the primary goals of ABC care is to avoid unnecessary and costly imaging and the risks associate with it, including unnecessary, ineffective, and potentially morbid surgeries.

[figure not shown]

Figure 4. The ABC Stepped Care Approach

The conditions targeted by ABCs include those that cause CLBP directly (hip OA⁶⁶, SIJS⁶⁸, myofascial pain⁶⁷, lumbar spinal stenosis⁶⁹, leg length discrepancy⁵⁴); those that impair pain modulation, compound CLBP-associated disability and that themselves can cause disability (fibromyalgia³⁰, depression²¹, anxiety²¹, maladaptive coping [i.e., pain catastrophizing⁷¹ and/or fear avoidance beliefs⁷⁰], insomnia²³, dementia⁷²); and those that can mimic radiculopathy (greater trochanteric pain syndrome⁷³, myofascial pain⁷⁴). While our screening procedures exclude Veterans with possible dementia (based on the Mini Mental State Examination), those with possible mild cognitive impairment (MCI) will be included. As MCI and dementia are on a continuum, providers may wish to apply elements of the published Dementia protocol to those that screened positive for MCI.

Participants:

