5.5 Study Evaluations

Screening Procedures (Appendix 7): Telephone screening by the RC (approved via a waiver of consent) using a structured questionnaire will determine participant eligibility, i.e., CLBP, ability to participate for up to 12 months, no red flags or prohibitive communication impairment, and no acute medical or psychiatric illness. If the screening procedures indicate that the Veteran is eligible, (s)he will be invited to come in for on-site baseline testing. After the participant has signed the HIPAA and Informed Consent documents they are considered enrolled. Then, the RC will administer the MMSE and those who fail (i.e., screen positive for dementia with a score $<$ 24) will be excluded and their PCP notified. We use the MMSE because it has been

studied extensively, has good diagnostic accuracy (sensitivity 0.85, specificity 0.9) and it takes only 5 to 7 min to administer.⁸⁵ Then a doctor who is part of this study will perform a Red Flags Screening. After this is complete, participants will be considered active participants in this study. Beyond the data measures that must be collected on site (MMSE, gait speed, and Red Flags Screening by provider), the remaining may be collected over the telephone or on site.

Baseline Testing (Appendix 8) - On all enrolled participants, RCs will collect a set of established measures that assess constructs relevant to older adults and have low participant burden, as shown in Table 6.

1. The **Oswestry Disability Index (ODI)**: Our main outcomes measure, the ODI assesses interference of pain with function.¹²
2. The **Minimal Data Set (MDS)**, recommended by the NIH Task Force on research standards for CLBP, measures pain severity and interference with daily activities, widespread pain, prior CLBP treatments, overall physical function, depressive symptoms, sleep, psychological maladaptation (i.e., fear-avoidance beliefs and catastrophizing), alcohol/drug use, cigarette smoking, demographics (age, race, ethnicity, gender, education, marital status), height and weight.⁴
3. The **PROMIS 29** collects items not already included in the MDS - anxiety symptoms, fatigue, and participation in social roles and activities.¹⁴ The full PROMIS 29 will be administered during follow-up.
4. **Other key cofactors** that may impact outcomes, and are relevant to older Veterans:
 - a. Medical comorbidity will be measured by self-report with the Duke comorbidity index.⁸⁶

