Perceived Intervention Value			final month
Global Impression of Change			final month

below. All statistical analyses will be performed using SAS® version 9 (SAS Institute, Inc., Cary, North Carolina) by the study statistician [name]. Participant flow will be summarized using a CONSORT diagram.⁹⁸ Data will be summarized by intervention arm and time point as well as baseline to follow-up change using appropriate descriptive statistics. First, the baseline participant characteristics will be compared between the two arms. Any significant differences will be noted and accounted for as covariates in the sensitivity analyses. Second, primary and secondary analyses to address the aims will be performed as outlined below using multiple imputation for missing data. The primary analysis will be performed to test the primary hypotheses H1.1 about the ODI. Secondary analyses will be performed for remaining hypotheses, secondary outcomes and other exploratory analyses. Third, we describe below our primary approach to missing data and a set of sensitivity analyses by including additional covariates, ignoring missing data, and reasonable alternative statistical modeling strategies to assess the robustness of our findings.

Baseline Comparison:

Due to the large sample size and the randomization scheme balanced with respect to site, it is highly unlikely that baseline participant characteristics will be significantly different between the arms. If we do find any, they will be included as covariates in the sensitivity analyses. We will not alter the primary analysis to preserve its a priori nature and predictability. We will use independent samples t- or Wilcoxon rank sum tests, as appropriate based on distributional properties, to compare continuous baseline characteristics between the intervention arms. For categorical baseline participant characteristics, we will use chi-square and Fisher's exact tests, as appropriate. Statistical significance of the intervention term will be interpreted as indicating the need to include them as covariates in sensitivity analyses.

Aim 1 Primary Analysis:

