We will fit a linear mixed model with baseline to follow-up change in ODI score as the dependent variable; intervention arm (ABC/UC), follow-up time point (6/12 months) and their interaction as fixed effect of main interest; baseline ODI as a fixed effect covariate; and a participant random effect to account for multiple repeated assessments of the same participant over time. The statistical significance at $\alpha=0.05$ of the ABC vs UC means contrast at the 6-month point will serve as the formal test of the primary hypothesis H1.1. Upon confirming the H1.1 primary hypothesis, we will compute the number-needed-to-treat (NNT) as the reciprocal of the between-intervention difference in percentages of those showing a meaningful ODI improvement above its MCID.

Aim 1 Secondary Analyses:

To characterize the intervention actually received under ABC care, we will describe the conditions identified, further evaluations/initiated treatments and their responses recorded in the form that tracks response to treatment and additional management plans (see Appendix 12). We will employ the same analytic strategy described above for ODI (under primary analysis) for our secondary continuous outcomes pain severity, quality of life and falls efficacy. The statistical significance of the ABC vs UC means contrast at the 6- and 12-month points will serve as the formal tests of the secondary hypotheses H1.2.

Measures of healthcare utilization between 6 and 12 months in H1.3 (prescriptions/refills of opioids and inappropriate medications for elderly, invasive procedures, emergency room/hospital visits) are mostly in the form of counts. As such, we will fit a series of generalized linear models with each count utilization outcome as the dependent variable, a negative binomial distribution to account for any over dispersion and a logarithmic link function for the count outcome, actual person-time of exposure with opportunity for reporting utilization outcome as an offset, and intervention arm (ABC/UC) as the independent factor of interest. Intervention arm incident rate ratios and their statistical significances will constitute tests of H1.3.

Aim 2 Analyses:

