We will perform a series of sensitivity analyses to ensure the robustness of our results against various assumptions. One such analysis will involve inclusions of baseline participant characteristics significantly different between groups as additional covariates in the linear mixed and generalized linear models above. Another will involve sensitivity of results to missing data handling techniques. In addition, if analyses of residuals from the models show violations of statistical assumptions, we will consider fitting models after Box-Cox transforming¹⁰¹ the continuous variables. Finally, a reasonable alternative to the proposed negative binomial models for count data representing healthcare utilization measures is the zero-inflated Poisson model.¹⁰² We will examine the sensitivity of our findings for utilization outcomes against this alternative modeling strategy.

Sample Size Justification and Statistical Power:

Planned sample size is 310 participants. Prior data and assumptions include a between-subject standard deviation of 18 points for pre- to post-intervention change in the primary outcome ODI¹⁰³; a conservative estimate of a minimally clinically important difference (MCID) of 7 points¹⁰⁴; a conservative dropout rate of 15% from other back pain trials¹⁰⁵; using published methods implemented in commercial software (PASS 2012®, Number Cruncher Statistical Systems, Kaysville, Utah), with 310 patients and 280 anticipated completers, we will be able to detect an observed primary outcome difference as small as 7 points with 90% power in a 2-tailed test at the $\alpha=0.05$ level.

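### The primary ODI model adjusts only for baseline ODI; naming a few already-collected baseline predictors and site in advance could gain a little precision at almost no cost

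*Combined protocol and SAP*

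**What the plan says.** - **What is measured, and when.** Section 5.5 (Baseline Testing) applies the baseline set to all enrolled participants, and Randomization and Blinding places randomization after it. Item 4 covers comorbidity (Duke index), pain and other medications, social support, opioid difficulties and suicidality, as cofactors "that may impact outcomes, and are relevant to older Veterans". Item 2, the NIH minimal data set, supplies depressive symptoms, the fear-avoidance and catastrophizing items, and age.
- **What is said about prognosis.** Section 5.1 puts depression, anxiety and maladaptive coping among conditions that "compound CLBP-associated disability and that themselves can cause disability".
- **The primary model.** Section 5.6 (Aim 1 Primary Analysis) has arm, time, their interaction, a participant random effect and "baseline ODI as a fixed effect covariate". The continuous H1.2 outcomes follow the same strategy. No site term appears, although randomization is stratified by site.
- **Other routes for covariates.** Under Baseline Comparison and Sensitivity Analyses, a baseline variable is added only if it differs significantly between arms, and only in a sensitivity analysis. The reason given is: "We will not alter the primary analysis to preserve its a priori nature and predictability". Aim 2 uses baseline disability, anxiety/depression, mild cognitive impairment and obesity as exploratory effect modifiers.

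**The concern.** Adjusting for a pre-randomization variable that predicts the outcome leaves the ABC versus UC contrast unbiased and shrinks its residual variance. The trial pays to collect several candidates on everyone, but none has a prespecified role in the H1.1 test.

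The one route by which they can enter an adjusted Aim 1 model, a significant baseline difference, selects on chance imbalance and not on prognostic strength. A strong predictor that happens to be balanced would never be used, while a weak one that is imbalanced would be.

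At stake is some width of the H1.1 confidence interval and a few points of power. The validity of the test is not at stake.

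**Working it through.** **Inputs from section 5.6 (Sample Size Justification).** Difference 7 points; "a between-subject standard deviation of 18 points for pre- to post-intervention change in the primary outcome ODI"; 280 completers, so 140 per arm; two-sided 0.05. No covariate adjustment is credited in the SD of 18.

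**Step 1: reproduce the plan's figure.** SE = 18 × √(2/140) = 2.151, and 7/2.151 = 3.25. The noncentral t with 278 degrees of freedom gives power 90.0%. This matches the plan's statement of a difference "as small as 7 points with 90% power in a 2-tailed test".

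**Step 2: the planned model already goes beyond this.** It adjusts for baseline ODI. If baseline ODI correlates r with ODI change, the residual SD is 18 × √(1 − r²). The documents give no r, so I show 0, 0.3 and 0.5 as assumptions:
- r = 0: SD 18.00
- r = 0.3: SD 17.17
- r = 0.5: SD 15.59

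**Step 3: add the covariates.** Let R² be the share of the variance left after baseline ODI that they explain. The documents give no value; 5 to 15% is an assumption. The residual SD becomes 18 × √(1 − r²) × √(1 − R²). Power with 280 completers:

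| r (assumed) | R² = 0 (planned model) | 5% | 10% | 15% | Gain, 5–15% |
|---|---|---|---|---|---|
| 0 | 90.0% | 91.4% | 92.8% | 94.0% | 1.4–4.0 points |
| 0.3 | 92.5% | 93.7% | 94.8% | 95.8% | 1.2–3.3 points |
| 0.5 | 96.3% | 97.0% | 97.7% | 98.2% | 0.7–1.9 points |

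The proportional fall in SE is 1 − √(1 − R²), whatever r is: 2.5%, 5.1% and 7.8%. At r = 0.3 the SE goes from 2.05 to 2.00, 1.95 and 1.89. In sample-size terms, 280/(1 − R²) − 280 gives about 15, 31 and 49 extra completers.

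**Step 4: the price.** Each added term costs a degree of freedom. With k terms the break-even R² is about k/(N − 4). For depressive symptoms, the fear-avoidance item, the catastrophizing item, the Duke index and age, k = 5 and 5/276 = 1.8%. Counting two terms for three sites, k = 7 and 7/276 = 2.5%. Below roughly 2% there is nothing to gain. The table does not deduct this cost.

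**Step 5: sensitivity to completers.** The plan's own 15% dropout gives 310 × 0.85 = 263.5 completers, not 280. That discrepancy is a separate matter. At 263, the same formulas give gains of 1.5–4.5 points (r = 0), 1.3–3.8 (r = 0.3) and 0.9–2.4 (r = 0.5), so the picture does not change.

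**The case against.** The strongest defence is that nothing is broken. Under randomization the contrast is unbiased, its type I error already allows for chance imbalance, and a parsimonious model with the outcome's baseline is an accepted choice. All of that stands.

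The documents also do not establish the size, or even the existence, of a gain. Three stronger readings are tempting, and none is supported:

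- **That the protocol declares all these variables prognostic.** The phrase "that may impact outcomes, and are relevant to older Veterans" heads item 4 only and says no more than that they may matter. Of the list proposed here it covers only the Duke index. Depressive symptoms and the coping items rest on section 5.1, and age rests on neither. Item 4 is not uniformly available either: the opioid difficulties scale is given only to opioid users.
- **That precision is certainly being lost.** Section 5.1 speaks of causing or compounding disability, which concerns its level. The model needs prediction of ODI change once baseline ODI is included. Some titles in the reference list point towards prognostic value (reference 86 on comorbidity adjustment for functional outcomes, reference 71 on catastrophizing as a prognostic factor), but no strength is given.
- **That the whole gain starts from 90%.** That figure uses an unadjusted SD, whereas the planned model already includes baseline ODI. The 1.4–4.0 point row therefore applies only if baseline ODI explains nothing.

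One argument for leaving the model alone does not stand. Keeping the primary analysis a priori rules out covariates chosen after looking at the data. It does not rule out a list fixed beforehand, which is equally predictable.

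**Conclusion.** This is a cheap improvement of low priority. The H1.1 test is valid as written, and its stated power reproduces without these variables.

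The model may leave a little efficiency unused. With 280 completers and an assumed R² of 5 to 15% after baseline ODI, the SE would fall by about 2.5 to 8%. Power would rise by 1.2–3.3 points at an assumed correlation of 0.3 between baseline ODI and change, by 0.7–1.9 points at 0.5, and by at most 1.4–4.0 points if that correlation is zero. If the true R² is under about 2%, the gain is nil. Both R² and the correlation are assumptions.

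Site belongs in the model on different grounds: it is the stratification factor, so its inclusion follows from the design and does not depend on these figures.

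**What to change.** In section 5.6, Aim 1 Primary Analysis, before any outcome is compared by arm, name a short fixed list in addition to baseline ODI:

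- recruitment site;
- baseline depressive symptoms;
- the fear-avoidance item and the catastrophizing item;
- the Duke comorbidity index;
- age.

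Use the same list for H1.2 with each outcome's own baseline. Keep the model with the outcome's baseline alone as a sensitivity analysis.

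**Cost:** SAP wording only. No new data, visits or participants are needed. It uses about 5 degrees of freedom plus 2 for site, and the list must be frozen in advance.

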5.6 Data Analysis

Data Management: A summary of the baseline and follow-up data is provided in Table 7. Data will be collected using paper forms. Completed data forms will be entered into a secure electronic database on a VA network server with regular server backup. The PI will work with the VAPHS research team to oversee all aspects of data management in accordance with policies and procedures outlined in VHA Handbook 1200.12. Only research team members at participating sites will have access to personal information needed for conducting informed consent procedures and participant tracking. Data collected on paper forms and any identifiable information will be stored in the Research Coordinator's office at each site, under double lock and key. All participants will be assigned unique synthetic identifiers that will appear on forms, files and serve as a non-identifiable index in database tables. Only de-identified data will be entered into the secure electronic database. There will be no data fields in which to enter individually identifiable information electronically, except the synthetic participant study IDs. Data entry will include double data entry checks. All research desktop computers will be encrypted. The encryption software will be Federal Information Process Standards (FIPS) 140-1,2 compliant. Data collected for this study will be kept in compliance with VHA regulations forbidding the destruction of research records.

Data Analysis:

Overview:

The study Statistician, [name] will be in charge of data analysis along with the PI. [name] will be sent only de-identified data as described above. We will perform all main analysis based on **intention-to-treat** following the a priori plans outlined

Table 7. Baseline and Follow-up Data

Measure	Timepoint		
	Baseline	Q3 month*	Q month
Oswestry Disability Index (Primary Outcome)	X	X	
NIH Task Force Minimum Data Set	X		
Quick Mild Cognitive Impairment (QMCI) screen	X		
Medical Comorbidity (Duke Comorbidity Index)	X		
Social Support (MOS Social Support Scale)	X		
Prescribed Opioids Difficulties Scale	X		
Pain Self Efficacy Questionnaire	x		
Gait Speed	X		
Life Space Assessment	X	X	
0-10 Numerical Rating Pain Scale	X	X	X
PROMIS-29	X	X	
Falls Efficacy Scale-international Short Form	X	X	
PROMIS Global Health Scale	X	X	
Veterans RAND 12 Item Health Survey (VR-12)	X	X	
Treatment History	X		
Healthcare Utilization (pain medication, emergency room use, hospitalization)	X	X	X
Medications	X		final month
Perceived Intervention Value			final month
Global Impression of Change			final month

below. All statistical analyses will be performed using SAS® version 9 (SAS Institute, Inc., Cary, North Carolina) by the study statistician [name]. Participant flow will be summarized using a CONSORT diagram.⁹⁸ Data will be summarized by intervention arm and time point as well as baseline to follow-up change using appropriate descriptive statistics. First, the baseline participant characteristics will be compared between the two arms. Any significant differences will be noted and accounted for as covariates in the sensitivity analyses. Second, primary and secondary analyses to address the aims will be performed as outlined below using multiple imputation for missing data. The primary analysis will be performed to test the primary hypotheses H1.1 about the ODI. Secondary analyses will be performed for remaining hypotheses, secondary outcomes and other exploratory analyses. Third, we describe below our primary approach to missing data and a set of sensitivity analyses by including additional covariates, ignoring missing data, and reasonable alternative statistical modeling strategies to assess the robustness of our findings.

Baseline Comparison:

Due to the large sample size and the randomization scheme balanced with respect to site, it is highly unlikely that baseline participant characteristics will be significantly different between the arms. If we do find any, they will be included as covariates in the sensitivity analyses. We will not alter the primary analysis to preserve its a priori nature and predictability. We will use independent samples t- or Wilcoxon rank sum tests, as appropriate based on distributional properties, to compare continuous baseline characteristics between the intervention arms. For categorical baseline participant characteristics, we will use chi-square and Fisher's exact tests, as appropriate. Statistical significance of the intervention term will be interpreted as indicating the need to include them as covariates in sensitivity analyses.

Aim 1 Primary Analysis:

We will fit a linear mixed model with baseline to follow-up change in ODI score as the dependent variable; intervention arm (ABC/UC), follow-up time point (6/12 months) and their interaction as fixed effect of main interest; baseline ODI as a fixed effect covariate; and a participant random effect to account for multiple repeated assessments of the same participant over time. The statistical significance at $\alpha=0.05$ of the ABC vs UC means contrast at the 6-month point will serve as the formal test of the primary hypothesis H1.1. Upon confirming the H1.1 primary hypothesis, we will compute the number-needed-to-treat (NNT) as the reciprocal of the between-intervention difference in percentages of those showing a meaningful ODI improvement above its MCID.

Aim 1 Secondary Analyses:

To characterize the intervention actually received under ABC care, we will describe the conditions identified, further evaluations/initiated treatments and their responses recorded in the form that tracks response to treatment and additional management plans (see Appendix 12). We will employ the same analytic strategy described above for ODI (under primary analysis) for our secondary continuous outcomes pain severity, quality of life and falls efficacy. The statistical significance of the ABC vs UC means contrast at the 6- and 12-month points will serve as the formal tests of the secondary hypotheses H1.2.

Measures of healthcare utilization between 6 and 12 months in H1.3 (prescriptions/refills of opioids and inappropriate medications for elderly, invasive procedures, emergency room/hospital visits) are mostly in the form of counts. As such, we will fit a series of generalized linear models with each count utilization outcome as the dependent variable, a negative binomial distribution to account for any over dispersion and a logarithmic link function for the count outcome, actual person-time of exposure with opportunity for reporting utilization outcome as an offset, and intervention arm (ABC/UC) as the independent factor of interest. Intervention arm incident rate ratios and their statistical significances will constitute tests of H1.3.

Aim 2 Analyses:

The goal is to explore whether ABC vs UC differences in improvement vary across participant subgroups of interest (effect modification). We will add each of the subgroups (based on baseline CLBP-associated disability, anxiety/ depression, mild cognitive impairment and obesity) and associated subgroup \times intervention group interaction effects as additional fixed effects in the above statistical models. Rigorous methodological guidelines for subgroup analyses require significant interaction effects for making conclusions of differential intervention effects in subgroups.⁹⁹ As such, we will first construct difference-in-difference type means contrasts representing the difference in ABC vs UC effects in different subgroups at each of the follow-up time points. If and only if the said interaction contrast is significant, we will estimate ABC vs UC differences and

their statistical significance within those subgroups.

Missing Data:

The best approach for handling missing data is to prevent it. We will use the methods described earlier to retain participants and prevent missing data. Despite our best efforts, missing data will occur. We will clearly document those with missing data and reasons in the CONSORT diagram, and compare those with missing data to complete data with respect to available data. Statistical guidelines for handling missing data recommend methods such as multiple imputation, which considers the uncertainty involved in imputing missing data.¹⁰⁰ Multiple imputation is arguably the best available objective method to analytically account for missing data under the ignorable or missing-at-random (MAR) assumption. Specifically, we will generate M=5 imputed values for each missing value, analyze the 5 datasets as though complete, and finally combine the results appropriately so that they reflect the uncertainty involved in imputation. SAS® MI and MIANALYZE procedures will be used. Other approaches to missing data, including the naïve approaches of ignoring the missing values and last-value-carried-forward (LVCF) will also be considered in sensitivity analyses and robustness of the results to using these approaches will be examined.

Sensitivity Analyses:

We will perform a series of sensitivity analyses to ensure the robustness of our results against various assumptions. One such analysis will involve inclusions of baseline participant characteristics significantly different between groups as additional covariates in the linear mixed and generalized linear models above. Another will involve sensitivity of results to missing data handling techniques. In addition, if analyses of residuals from the models show violations of statistical assumptions, we will consider fitting models after Box-Cox transforming¹⁰¹ the continuous variables. Finally, a reasonable alternative to the proposed negative binomial models for count data representing healthcare utilization measures is the zero-inflated Poisson model.¹⁰² We will examine the sensitivity of our findings for utilization outcomes against this alternative modeling strategy.

Sample Size Justification and Statistical Power:

Planned sample size is 310 participants. Prior data and assumptions include a between-subject standard deviation of 18 points for pre- to post-intervention change in the primary outcome ODI¹⁰³; a conservative estimate of a minimally clinically important difference (MCID) of 7 points¹⁰⁴; a conservative dropout rate of 15% from other back pain trials¹⁰⁵; using published methods implemented in commercial software (PASS 2012®, Number Cruncher Statistical Systems, Kaysville, Utah), with 310 patients and 280 anticipated completers, we will be able to detect an observed primary outcome difference as small as 7 points with 90% power in a 2-tailed test at the $\alpha=0.05$ level.

